7.2 Independent Review of Adverse Events

Objective review of adverse events (Stent Thrombosis, Cardiac Death, Myocardial Infarction, and TLR/TVR) will be conducted by a third party (medical professional) up to 3 years post index procedure. These events will be reviewed based on ARC definition. QCA results from angiographic core-lab will be provided to the reviewer as necessary.

7.3 Analysis of Results

Collected data will be analyzed and Annual Report will be submitted according to "Survey Report on new medical device usage" (Japan Pharmaceutical and Food Safety Bureau Notice 1224, no. 4, dated December 24, 2010). Subgroup analyses will be conducted as necessary to evaluate safety and efficacy of the device, and included in the resubmission report.

1.1. Purpose of investigation

This survey is a post-marketing drug use results survey (hereinafter referred to as "this survey") conducted by marketers or foreign exceptional approval holders of medical devices specified in Article 14, Paragraph 1 of the Pharmaceutical Affairs Law (Law No. 145 of 1960) and Article 14-6, Paragraph 4 of the Law (including cases where these provisions are applied mutatis mutandis in Article 19-4 of the Law). In order to ensure the safety of new medical devices, the frequency of defects and the status of defects are monitored. The objective is to collect data on efficacy and safety for reexamination.

This survey shall be conducted in compliance with the Ministerial ordinance for Standards for the Conduct of Post-marketing Surveys and Studies of Medical Devices (MHLW ordinance No. 38 of March 23, 2005, hereafter referred to as the "GPSP ordinance").

1.2. Subjects

Based on GPSP ordinance, this survey does not have specific inclusion/exclusion criteria and will enroll patients with ischemic heart disease who may be treated with XIENCE PRIME SV drug-eluting stents (approval number: 22500BZX00070000, approval date: March 7, 2013) (hereinafter referred to as the device). As part of the treatment in the real-world clinical setting at each study site, patients who are treated with the device in principle and are available for 8-month angiographic follow-up and 1-year clinical follow-up will be included.

In addition to the study populations enrolled for the first time in this survey, patients who participated in the Clinical Evaluation of AVJ-09-385 Coronary Stents in Japanese Subjects in AVJ-09-385 Coronary Stent Study, which was conducted as a clinical trial in product, will also be included. The 5-year follow-up period after the procedure was conducted as a "clinical trial" until the approval date of marketing. However, the handling of this clinical trial was checked with the Pharmaceuticals and Medical Devices Agency (PMDA), and it was decided that the clinical trial should be continued as a "clinical trial results survey after the approval of marketing" and "clinical trial completion date (follow-up observation) may be the approval date of marketing," so the clinical trial should be continued as a "clinical trial results survey" after the approval of marketing.

1.3. Estimated number of registrations

This survey aims to enroll approximately 300 patients at approximately 30 institutions.

Previous studies predicted a 1-year MACE (Combined Assessment of Cardiac Death, Myocardial Infarction and Ischemic Target-Lesion Revascularization) of 15% in this survey. When 300 patients were enrolled, 1/2 of the 95% two-sided confidence interval for an MACE rate of 15% was 4.2%, corresponding to 28% of the expected MACE rate of 15%. Within this range, the efficacy and safety of

the device can be sufficiently assured in the real-world clinical setting in Japan.

A total of 62 subjects continued to participate in the clinical study described above.

1.4. Treatment of patients

The treatment plan should follow the standard of care when performing coronary interventions at each center at the discretion of the physician.

Physicians should discuss patient treatment with reference to warnings, contraindications, and PRECAUTIONS included in the updated package insert.

The final decision for antiplatelet therapy will be made by the doctor, but the package insert for the device requires that subjects at low risk of bleeding receive aspirin indefinitely and thienopyridines (e.g., clopidogrel, ticlopidine) for at least 6 months. In addition, XIENCE PIME package insert states that thienopyridines will be administered for at least 12 months to subjects with XIENCE PRIME in place. Refer to the updated version of the thienopyridine package insert before starting treatment for each patient. Laboratory tests and clinical observations necessary to evaluate the adverse reactions of thienopyridines should be conducted in accordance with the package insert.

2. Definition of analysis set and abbreviations

2.1. Analysis population definitions

No	Definition name	Definition Content
1	Survey period	March 7, 2013 - December 31, 2019
2	Date of data lock (snapshot)	Data lock (snapshot) dates for annual reports are as follows 1st: September 5, 2013 2nd: September 5, 2014 3rd: September 5, 2015 4th: September 5, 2016 5th: September 5, 2017 6th: September 5, 2018 7th: September 5, 2019 Reexamination: September 5, 2019 Subjects with fixed CRFs by the time of data lock.
3	CRF-collected subjects	Subjects whose CRFs were fixed
4	Subjects who are out of the survey	The cases who were treated with out-of survey stent, among CRF-collected subjects in newly enrolled patients.
5	Subjects to be investigated	The cases excluding subjects who are out of the survey among CRF-collected subjects.
6	Non-stent implanted subjects	Among the subjects studied, the cases in which the stent to be investigated could not be placed.
7	Stenting subjects	Among the investigated subjects in newly enrolled patients, the cases who were treated with investigated stent Investigated subjects transitioning from the pre-market study.
8	Newly enrolled patients	Patients enrolled for the first time in this survey.
9	Patients transitioning from the study	Patients who participated in the Clinical Assessment of AVJ-09-385 Coronary Stenting in Japanese Subjects in AVJ-09-385 Coronary Stenting Trial.

No	Definition name	Definition Content
10	Observation status	
The number of follow-up examinations will be calculated by observation time point based on the actual status of follow-up examinations at the observation time point.
 
However, the following criteria should be followed for withdrawals.
 
 • In the case of withdrawal due to "inability to contact" the subject shall be assessed by identifying the time point of dropout based on the scheduled date * and observing the subject up to the previous time. 
However, if the contact is conducted at the relevant time point before "contact is not possible" is established, the observation shall be carried out until that time.
 
 • Other withdrawal dates will be the last follow -up date. 
However, "death" shall be specified based on the expected date. In addition, the time point for "other than death" should be specified after considering the range of adoption of the scheduled date.
 
 • Even if there are no dropouts on the questionnaire, if no follow -up is performed twice at 1 year or later, it is considered dropouts, and the date of first unsupervised follow-up (expected date) is considered the final observation (e.g., if 4-year and 5-year observations are not performed, 1460 days are considered the final observation date). 
※Expected date (scope of employment) 1 year: 365 days (365 ± 30 days) 2 years: 730 days (730 ± 30 days) 3 years: 1095 days (1095 ± 30 days) 4 years: 1460 days (1460 ± 30 days) 5 years: 1825 days (1825 ± 30 days)

11	Analysis set by time point	
The following conditions will be added to the observation status to identify the number of patients included in the analysis at each time point:
 
 • Cases in which death, myocardial infarction, or total revascularization occurred will be included in the analysis at all time points.

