2.3 Number of Patients to be Registered

The goal is to register 300 patients from approximately 30 sites.

MACE (composite of cardiac death, myocardial infarction and ischemia-driven target lesion revascularization) rate of this surveillance is expected to be 15%, based on past trials. For 300 patients, half of 95% confidence interval of MACE rate of 15% is 4.2%. This is 28% of expected MACE rate of 15%. This range will be enough to evaluate safety and efficacy of XIENCE PRIME SV in real world practice in Japanese hospitals.

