5.5 Eight Months Follow-up

1) General Information

- Contact Method
- Contact Date
- Reportable adverse event since the last follow-up
- Change or termination of antiplatelet therapy
- Device Deficiency
- Follow-up Angiogram
- Ischemic Symptoms
- Revascularization

2) Angiographic Information

Angiographic corelab analysis data will be adopted when it is applicable.

- Lesion Length (if restenosis exist)
- Reference Vessel Diameter

- %DS

5.6 1~5 Years Follow-up (Every Year)

- Contact Method
- Contact Date
- Reportable adverse event since the last follow-up
- Change or termination of antiplatelet therapy
- Device Deficiency

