Summary statistics (incidence)	
Incidence rates (%), number of events (molecules), number of populations analyzed (denominators) and 95% confidence intervals of frequencies are calculated. However, cases in which the relevant variable is a missing value are also included in the population of the incidence calculation.
 
4.3 Population numbers for antiplatelet therapy and 4.4 adverse events are specified as follows.
 
4.3 Antiplatelet therapy
 
Newly enrolled patients will be included.
 
Pre-procedure: Case of stenting
 
Procedure Day to Discharge Day: Stenting Cases
 
Procedural Day ~ 8 Months Observation Day: 8 Months Analyzed by Case Time Point of Stenting
 
Procedural Day-1 Year Observation Day: 1 Year Analyzed by Time Point of Stent Implantation
 
Procedural Day ~ 2 Years Observation Day: 2 Years Analyzed by Time Point of Stent Implantation
 
Procedural Day ~ 3 Years Observation Day: 3 Years Analyzed by Time Point of Stent Implantation
 
Procedural Day ~ 4 Years Observation Day: 4 Years Analysis Population by Time Point of Stent Implantation
 
Procedural Day ~ 5 Years Observation Day: 5 Years Analysis Population by Time Point of Stent Implantation
 
4.4 Adverse Events
 
Newly enrolled patients will be included.
 
Procedural Day + 3 Day: Stent Case
 
Procedural Day +4 Days or Beyond to Discharge Day: Stenting Cases
 
The day after discharge to the observation day of Month 8: 8 months for analysis by time point of stenting
 
Observation day of 8 months to 1 year: 1 year for analysis by time point of stenting
 
Observation day 1 to 2 years after the observation day of 1 year: 2 years for analysis by time point of stented patients
 
Observation day of 2-year observation day to 3-year observation day: 3 years for analysis by time point of stented patients
 
Observation day of the following day of observation in Year 3 to Year 4: 4 years for analysis by time point of stent implantation
 
Observation day of the following day of observation in Year 4 to Year 5: 5 years for analysis by time point of stenting
 
During hospitalization: patients with stents
 
Until 8 months: Stent implantation
 
Until 1 year: Stent implantation
 
Until 2 years: Cases of stenting
 
Until 3 years: Cases of stenting
 
Until 4 years: Cases of stenting
 
Until the end of the survey: patients undergoing stent placement
 
Overall post-procedure: stenting cases

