
Items	Calculation method, etc.
Confidence interval for the incidence	
Accurate confidence intervals based on Clopper-Pearson method will be calculated.
 $\pi_L = \frac{v_2}{v_2 + v_1 F_{\alpha/2}[v_1, v_2]} \quad v_1 = 2(n - x + 1), v_2 = 2x$ $\pi_U = \frac{v_1 F_{\alpha/2}[v_1, v_2]}{v_2 + v_1 F_{\alpha/2}[v_1, v_2]} \quad v_1 = 2(x + 1), v_2 = 2(n - x)$
Age (years)	The actual age at the date of the procedure (date of registration) is calculated from the date of birth (date is read in one day).
Body Mass Index	Calculated from weight (kg) and height (cm). Body Mass Index = Weight (kg)/ (Height (cm)/100) ²
Acceptable range on the observation day	
Observation day of 8 months: ± 30 days 8 months after the procedure day Observation day 1 year: ± 30 days after the procedure day Observation date of 2 years: ± 30 days 2 years after the procedure date Observation day 3 years: ± 30 days 3 years after the procedure date Observation day in Year 4: ± 30 days 4 years after the procedure date Observation day in 5 years: ± 30 days 5 years after the procedure date
 
However, if it can be confirmed that there is no problem with the data quality, it should be adopted as the data at the time according to the time of the questionnaire, even if it is outside the range.

4. Statistical Analysis Content

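### The time-point sets used as denominators for the post-discharge interval rows of Tables 18 and 19 depend on outcome: the discharge-to-8-month rate is biased upward, and later rates can be biased either way

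*SAP*

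**What the plan says.** **Who is in a time point's set.** SAP 2.1, definition 10 (Observation status), has follow-up "calculated by observation time point based on the actual status of follow-up examinations at the observation time point". Its special rules cover withdrawals, and patients with two follow-ups not done at 1 year or later. It has no rule for a single missed visit followed by later contact. Its expected dates start at 1 year, so month 8 has none.

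**Who is added back.** Definition 11 (Analysis set by time point) adds one condition: "Cases in which death, myocardial infarction, or total revascularization occurred will be included in the analysis at all time points".

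**Where the sets are used.** SAP 3.2, Summary statistics (incidence), assigns them to the interval rows of section 4.4. The first reads "The day after discharge to the observation day of Month 8: 8 months for analysis by time point of stenting", and the rows up to year 5 follow the same pattern. The two earliest rows, the in-hospital row, the cumulative rows and the overall row use all stented patients instead. Section 4.3 (Table 17, antiplatelet therapy) uses the same time-point sets from month 8 on.

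**What a later contact collects.** Protocol 5.5 and 5.6 list, for the 8-month and every yearly follow-up, "Reportable adverse event since the last follow-up".

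**The concern.** Take two patients who both miss month 8 and are both reached at 1 year. One had a revascularization at some time; the other had no event. The 1-year contact covers the period back to the last follow-up, so both are known through month 8. Definition 11 keeps the first in the 8-month set, and nothing clearly keeps the second. Membership of the denominator therefore depends on the outcome that the row is meant to measure.

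The rule has three further effects:

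- The add-back applies at every time point. A patient who died in year 1 still counts in the denominators for years 2 to 5, where no further event is possible.
- Bleeding is a row of Table 19 but is not on the add-back list. A patient with only a bleed and a missed visit can leave the set together with that bleed. Bleeding therefore stands on a different footing from the other rows of the same table, although Protocol 6.1 names adverse events of antiplatelet medication as an important evaluation item.
- The intervals open and close on observation days. A patient without the visit has no such day, and for month 8 the SAP supplies no expected date to put in its place.

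At stake are planned safety tables in a survey whose purpose is to supply data for reexamination.

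**Working it through.** **1. The plan's own figure.** Protocol 2.3: "The goal is to register 300 patients from approximately 30 sites", the MACE "rate of this surveillance is expected to be 15%, based on past trials", and "half of 95% confidence interval of MACE rate of 15% is 4.2" per cent. SAP 3.2: "Accurate confidence intervals based on Clopper-Pearson method will be calculated". With 0.15 × 300 = 45 events in 300, Clopper-Pearson gives 11.16% to 19.55%, a half-width of 4.20%, and 4.2/15 = 28%. The figure reproduces. It concerns sample size and does not depend on the denominator rule.

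**2. Discharge to 8 months.** Let s be the share of patients who ever have death, MI or revascularization, and m the share of the others who miss the 8-month visit but are reached later. Assume 300 stented patients, a true interval rate of 10%, no deaths before discharge and no loss to follow-up. The documents give no value for s, m or the 10%; all are assumptions.

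Patients removed = 300 × (1 − s) × m. Reported rate = 10% / (1 − (1 − s) × m).

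| s | m | Removed | Reported rate |
|---|---|---|---|
| 0.35 | 0.05 | 9.8 | 10/0.9675 = 10.3% |
| 0.25 | 0.10 | 22.5 | 10/0.925 = 10.8% |
| 0.15 | 0.15 | 38.3 | 10/0.8725 = 11.5% |

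The first and last lines are the extremes over s = 15-35% and m = 5-15%. With m = 2%, the rate is 10.1% (s = 0.35) to 10.2% (s = 0.15).

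**3. Later intervals.** Let D be the number of deaths before the interval and F = 300 × (1 − s). The true denominator is 300 − D. The plan's denominator is 300 − mF, because earlier deaths are kept. So

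reported/true = (300 − D) / (300 − mF),

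which exceeds 1 only if mF > D. Take 2% deaths per year, m = 5% and s = 25%. Then mF = 0.05 × 225 = 11.25, the plan's denominator is 288.75, and D = 300 × (1 − 0.98^t), with t the interval's start in years. The last column varies deaths over 1-3% per year, m over 2-10% and s over 25-40%.

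| Interval | D | Reported/true | Range |
|---|---|---|---|
| Discharge to 8 months | 0 | 300/288.75 = 1.04 | 1.01 to 1.08 |
| 8 months to 1 year | 4.0 | 296.0/288.75 = 1.03 | 0.99 to 1.07 |
| Years 1-2 | 6.0 | 294.0/288.75 = 1.02 | 0.98 to 1.07 |
| Years 2-3 | 11.9 | 288.1/288.75 = 1.00 | 0.95 to 1.06 |
| Years 3-4 | 17.6 | 282.4/288.75 = 0.98 | 0.92 to 1.05 |
| Years 4-5 | 23.3 | 276.7/288.75 = 0.96 | 0.90 to 1.04 |

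The year 4-5 line is arithmetic only. Year 5 is the last scheduled contact, so m there has no scheduled visit to rest on; the downward pull from earlier deaths remains.

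**4. Break-even.** Setting mF = D with s = 25% to 40%: 3 earlier deaths cancel m = 1.3-1.7%, 6 cancel 2.7-3.3%, 12 cancel 5.3-6.7%, and 24 cancel 10.7-13.3%. The upward direction at 8 months therefore needs in-hospital deaths to be fewer than mF, which is 9.75 patients in the mildest line of step 2.

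**The case against.** **The exclusion is inferred.** The sentence in definition 10 governs the count of follow-up examinations, and no text names a single missed visit. The same definition treats only two misses at or after 1 year as dropout. Its example ends observation at day 1460 for a patient who missed years 4 and 5, so a missed visit does not by itself end observation. This stands as a caution. But that example fixes when observation ends for a dropout; it does not put a patient with one missed visit back into the set. SAP 3.2 keeps missing values in incidence denominators in general, but then gives section 4.4 its own populations. Its allowance for out-of-window data covers a late visit, not one that was never made.

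**The main estimates are untouched.** This is correct. The row up to 1 year, which matches the MACE rate used for sizing, uses all stented patients. The Kaplan-Meier analysis in SAP 4.4.4 does not use these sets. The interval rows are descriptive, and no test depends on them.

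**The size is assumed and modest.** Also correct. Even 11.5% lies inside the Clopper-Pearson interval for 30/300 (6.8% to 14.0%). But that interval describes sampling error, while this error comes from the rule itself and can be removed at little cost.

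**Two stronger readings go too far.** A reader might infer that all post-discharge rows are overstated. They need not be, because the rule that removes event-free patients also keeps the dead. A reader might also infer that well patients avoid the 8-month visit because it is an angiogram. The documents do not show this: Protocol 5.5 records contact method and date separately from the angiogram, and Protocol 2.2 says that patients known to be unable to return should not be registered.

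**Conclusion.** The concern holds in a limited form. As written, definitions 10 and 11 make the denominators of rows 3 to 8 in Tables 18 and 19 depend on outcome. For death, MI and revascularization from discharge to 8 months, the bias is upward: about 10.3% to 11.5% against 10%, under the assumptions in step 2 and with few in-hospital deaths. In later intervals the sign depends on missed visits against earlier deaths; for years 3-4 the ratio runs from 0.92 to 1.05. The year-5 row has no later scheduled visit through which a patient could be recovered. Bleeding is not protected and can be lost with the patient. For stent thrombosis, SAP 4.4.3 does not state interval rows for Table 20, so the point is not extended to it.

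The cumulative rows and the Kaplan-Meier estimates are not affected, and the documents give no ground to doubt the 1-year MACE rate on this account.

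**What to change.** Rewrite definition 11 in SAP 2.1. The set for an interval is the patients alive at its start who either

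- (a) have status known through its end, from any contact on or after the lower limit of the window for that time point, including a later visit or call; or
- (b) had the tabulated event, including bleeding, or died within the interval.

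Remove patients who died before the interval began. Limb (b) is essential: a rule resting on later contact alone would drop anyone who dies before the window opens, from numerator and denominator alike.

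Where the visit was missed, use the expected date as the interval boundary, and add a matching day for month 8 (SAP 4.4.4 already uses day 240). State whether Table 17, which shares these sets, follows the new definition.

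Cost: a few sentences in SAP 2.1 and one changed derivation program, with no new data. Two limits remain. Denominators may differ slightly between event rows. A patient lost event-free inside an interval still leaves its set, while one with the event stays; if such losses are more than a few, the Kaplan-Meier estimates are the better guide for the events that they cover.

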3. PMS DURATION

Duration of patient registration for the PMS will not be set, however the target is to complete registry by June 30th, 2014.

Annual reports will be submitted to PMDA every year. After the re-submission, data will continue to be collected until 5 year follow-up is complete for all patients.

Patient data from the following time points will be collected

- Baseline (before procedure)
- Procedure
- Post-Procedure through discharge
- 8 months follow-up (follow-up angiogram)
- 1 year post-procedure (site visit is recommended but telephone contact is allowed)
- 2 year post-procedure (site visit/telephone contact)
- 3 year post-procedure (site visit/telephone contact)
- 4 years post-procedure (site visit/telephone contact)

- 5 years post-procedure (site visit/telephone contact)

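### The two-missed-follow-ups dropout rule (SAP 2.1, definition 10) is not limited to gaps that run to the end, so read literally it removes event-free returning patients from the year 2 to 5 time-point denominators

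*SAP*

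**What the plan says.** Definition 10 in SAP 2.1 starts from a sound principle: follow-up is counted "based on the actual status of follow-up examinations at the observation time point". It then makes exceptions: "However, the following criteria should be followed for withdrawals". The last exception covers patients for whom the questionnaire records no dropout. It applies where no contact "is performed twice at 1 year or later, it is considered dropouts". The rule then assigns such a patient an end date: "the date of first unsupervised follow-up (expected date) is considered the final observation". One example is given: "if 4-year and 5-year observations are not performed, 1460 days are considered the final observation date". The expected dates are 365, 730, 1095, 1460 and 1825 days, each with a 30-day window either side.

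Definition 11 builds the analysis set for each time point from observation status, with one addition: "Cases in which death, myocardial infarction, or total revascularization occurred will be included in the analysis at all time points".

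SAP 3.2 uses these time-point sets as denominators for antiplatelet therapy from 8 months on (Table 17) and for the adverse-event intervals after discharge (Tables 18 and 19). The cumulative adverse-event rates use all stented cases. SAP 4.4.4 censors the Kaplan-Meier curves at the date of last contact or of withdrawal. Protocol section 3 schedules contacts every year up to "5 years post-procedure (site visit/telephone contact").

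**The concern.** The trigger is two missed annual contacts. The sentence does not ask that they be consecutive, that they be the last ones, or that the patient never be seen again. A programmer who codes it as written will classify as a dropout a patient whom the site did not report as one and who attended later contacts.

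Three things follow under that reading.

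- **Observation status.** Contacts attended after the first miss do not count in Table 2, so reported attrition is too high.
- **Interval rates.** Event-free returning patients leave the denominators for years 2 to 5, but definition 11 keeps patients with death, myocardial infarction or any revascularization in at every time point. The denominators lose only event-free patients, so interval rates for those events are pushed upward.
- **Bleeding.** Bleeding is reported in Table 19 and has no such add-back. A late bleed in a returning patient could be set against a denominator that excludes that patient. Protocol 6.1 names adverse events caused by antiplatelet medication as one of its two important evaluation items.

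The rule also sits badly beside another exception in definition 10. For loss through inability to contact, a contact made at the time point before the loss is established is credited. The two-miss rule has no such protection.

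**Working it through.** **The plan's own figure.** Code the rule literally: if two or more of the five annual contacts are missed, final observation day = 365 × (year of first miss). For misses at years 4 and 5 this gives 365 × 4 = 1460, as in the SAP.

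**The same rule on other patterns.**

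| Missed | Attended later | Final day | Attended contacts after it |
|---|---|---|---|
| 1, 2 | 3, 4, 5 | 365 | 3 |
| 2, 3 | 4, 5 | 730 | 2 |
| 2, 4 | 3, 5 | 730 | 2 |
| 3, 4 | 5 | 1095 | 1 |
| 4, 5 | none | 1460 | 0 |

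**Counting patterns.** Five contacts give 2^5 = 32 patterns. The rule fires in 32 − 1 − 5 = 26. In 4 of these the misses form one run to the end, so 26 − 4 = 22 have an attended contact after the assigned final day. In 10 of the 26 no contact follows the second miss, so 26 − 10 = 16 have the patient seen again after two misses.

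**Size.** The documents give no miss rate. Assume each annual contact is missed independently with probability q, and N = 300 (Protocol 2.3).

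- A = P(two or more missed) = 1 − (1−q)^5 − 5q(1−q)^4
- B = P(two or more missed, in one run to the end) = q²(1−q)³ + q³(1−q)² + q⁴(1−q) + q⁵
- C = P(two or more missed, none attended after the second) = 4q²(1−q)³ + 3q³(1−q)² + 2q⁴(1−q) + q⁵

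| q | A | B | C | 300(A−B): attended contact after first miss | 300(A−C): seen again after second miss |
|---|---|---|---|---|---|
| 5% | 0.0226 | 0.0023 | 0.0089 | 6.1 | 4.1 |
| 10% | 0.0815 | 0.0082 | 0.0318 | 22.0 | 14.9 |
| 15% | 0.1648 | 0.0168 | 0.0635 | 44.4 | 30.4 |

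At q = 2% the last column is 0.7 patients.

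**Effect on one denominator.** Among patients attending year 5, the rule removes those with two or more misses in years 1 to 4: 1 − (1−q)^4 − 4q(1−q)^3 = 1.4%, 5.2% and 11.0% at q = 5%, 10% and 15%. If all of them are event-free and the numerator is unchanged, the interval rate is multiplied by at most 1/(1 − 0.014) = 1.014, 1/(1 − 0.052) = 1.055 or 1/(1 − 0.110) = 1.12. These are upper bounds, because definition 11 returns some patients to the denominator. Year 1 and earlier are untouched: the earliest possible cut is the year 1 miss itself.

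**After the fix.** Limited to runs that reach the last contact, the rule marks no patient who is seen afterwards, and no attended contact falls after the final observation date. The 1460-day example is unchanged.

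**The case against.** The strongest reply is that the rule was meant only for silent loss to follow-up. It addresses patients with no recorded dropout, it speaks of a final observation, and its single example runs to the end. The English also reads like a translation, so much weight on the word for two occasions may be misplaced. This is fair: the intent may already be what the fix says. But the sentence overrides the actual-status count and does not contain the limit.

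The second reply concerns reach, and most of it stands. A reader might infer that follow-up after the first miss is discarded, or that late bleeding or stent thrombosis is lost. The documents do not say so.

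- No section deletes data or events after the final observation. SAP 3.2 even accepts data from outside the visit window when quality is confirmed.
- Cumulative rates, including the 1-year MACE rate behind the sample size, are taken over all stented cases and do not depend on observation status.
- Stent thrombosis is analysed on stented, newly enrolled cases (Table 20) and is a Kaplan-Meier event with no stated cut-off at the definition 10 date.
- Kaplan-Meier censoring for a returning patient can be the later contact. It changes only if the definition 10 date is used as the withdrawal date, and the SAP does not say whether it is.

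It is also true that the selective effect arises jointly with definition 11. The two-miss trigger itself does not look at outcomes. The survey is descriptive, so no test or error rate is involved.

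**Conclusion.** The point holds as a gap in a stated rule with a limited reach. Applied as written, definition 10 stops counting a returning patient at the first missed date. That affects Table 2, the year 2 to 5 denominators of Table 17 and the year 2 to 5 interval rows of Tables 18 and 19, with interval rates pushed upward for the events that definition 11 adds back. Cumulative rates are unaffected, and the Kaplan-Meier results are affected only under a link that the SAP leaves open.

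The size depends on a miss rate that the documents do not give. With independent misses at 5%, 10% or 15% per year and 300 patients, about 4, 15 or 30 are seen again after a second miss; 6, 22 or 44 have some attended contact after the first. The effect is negligible if misses are rare and visible in the late intervals if they reach 10%. Misses that cluster within patients would change these numbers.

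**What to change.** Amend definition 10 in SAP 2.1 to say:

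- the rule applies only to an unbroken run of two or more missed annual follow-ups that continues to the last scheduled contact (for an annual report, the last one due by that data lock);
- final observation is set from the first miss of that final run;
- every contact attended before that run counts by actual status.

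It is not enough to exempt patients seen after both misses. A patient who misses years 2 and 5 but attends years 3 and 4 would still be cut at day 730.

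In SAP 4.4.4, state whether the definition 10 date serves as the withdrawal date for censoring.

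The cost is one or two sentences and one condition in the program.
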